Specifically, DJ stent-related symptoms are urinary frequency (50–60%), sexual dysfunction (male, 42–82% and female, 30–86%), reduced work capacity (58%), urgency (57–60%), dysuria (40%), flank pain (19–32%), incomplete emptying (76%), suprapubic pain (30%), hematuria (25%), and reduced quality of life (QOL) in approximately 80% of the patients[4]. It is reported that an important factor of stent-related symptoms is the pressure transmitted to the renal pelvis during voiding and trigonal irritation by the intravesicular part of the stent[5]. For this reason, several attempts to minimize stent-related symptoms have recently been reported. Pharmacologic management is one such trial[6]. Symptoms of stent discomfort, including bladder irritation symptoms and flank pain or discomfort, are

generally treated with oral analgesics, such as narcotics and anti-inflammatory medications; however these medications are only moderately effective.

Alpha-blockers alleviate bladder irritation due to stents, resulting in reduced incidence of dysuria, frequency, and pain compared to placebo[7]. Additionally, solifenacina anticholinergic has also showed significant benefits in lower urinary tract symptoms, stent-related pain and hematuria[8].

RATIONALE:

A comparison between taking either an alpha-blocker (tamsulosin) or an anti-cholinergic (solifenacina) to alleviate ureteral stent-related symptoms after patients have undergone Dj stenting prior to Extracorporeal shockwave lithotripsy (ESWL), Ureteroscopy (URS) with DJ stent placement or Percutaneous nephrolithotomy (PCNL) with DJ stent placement has not yet been done in Pakistan.

OBJECTIVE:

In this study, we will assess the comparison between an alpha-blocker (tamsulosin) and an anti-cholinergic (solifenacina) in the treatment of ureteral stent-related symptoms using the Ureteral Stent Symptom Questionnaire (USSQ).

OPERATIONAL DEFINITIONS:

Extra corporeal shockwave lithotripsy: A procedure that utilizes shockwaves to fragment kidney stones that can then pass through the urinary tract and be removed.

DJ Stent: A double-J stent is a ureteral stent with curving ends that prevent the stent slipping into the bladder or the kidney and allows continuous drainage of urine into the bladder.

Lower Urinary Tract Symptoms: Lower urinary tract symptoms (LUTS) include voiding or storage symptoms such as:-

Hesitancy; Difficulty starting or maintaining a urine stream

Poor and intermittent stream; Intermittent urination is usually a sign of significant underlying bladder problem, most often incomplete bladder emptying can predispose to urinary tract infections, bladder stone formation, and renal insufficiency (damage to the kidneys).

Incomplete bladder emptying; Incomplete bladder emptying occurs when the muscles of the bladder are not able to squeeze properly to empty the bladder.

Frequency; Its normal and how many times is too frequent to urinate.

Urgency; Urinary urgency occurs when the pressure in the bladder builds suddenly, and it becomes difficult to hold in the urine.

Nocturia; the need for patients to get up at night on a regular basis to urinate

Alpha Blockers: Alpha blockers are also known as α -blockers or α -adrenoreceptor antagonists, are a class of pharmacological agents that act as antagonists on α -adrenergic receptors.

Anticholinergic: Anticholinergic drugs block the action of a neurotransmitter called acetylcholine. This inhibits nerve impulses responsible for involuntary muscle movements and various bodily functions. These drugs can treat a variety of conditions, from overactive bladder to chronic obstructive pulmonary disorder.

USSQ: Ureteral Stent Symptoms Questionnaire; a psychometrically valid measure to evaluate symptoms and impact on quality of life of ureteral stents.

HYPOTHESIS:

Solifenacin group have better outcome in comparison to Tamsulosin.

MATERIAL AND METHODS:

Study Design: Comparative study

Setting: Study will be conducted Department of Urology, Liaquat National Hospital Karachi. It will include the patients who had have complaints voiding symptoms like increased urinary frequency, urgency dysuria, incomplete bladder emptying and supra pubic pain.

Study Duration: 6 months after approval of synopsis.

Sampling Technique: non-probability consecutive sampling.

Sample size: The sample size is calculated by using the mean \pm SD of USSQ score i.e. 76 \pm 8 in tamsulosin group and 61 \pm 8.8 in solefinacin group. Open Epi Software is used for sample size calculation by taking power of test = 90% and confidence interval 95%, the total calculated sample is 14 patients (7 in each group). To improve the power the study, we will have 30 patients in each group.

Sample selection:

Inclusion criteria:

- Between the ages of 20 and 50 years,
- Patients who consented for unilateral DJ stent placement to relieve upper urinary tract obstruction caused by ureteric calculi or after ureteroscopic lithotripsy for ureteral calculi

Exclusion criteria:

- Having a history of LUTS before DJ stent placement
- Patients with bilateral DJ stent placement.
- Produced Stent related complications (displacement of stent)

DATA COLLECTION PROCEDURE:

Patients fulfilling the inclusion criteria presenting via outpatient clinic or emergency department at Liaquat National hospital, will be included in the study after taking informed and written consent. The study will start after the approval of synopsis by CPSP and Ethical and Review board of Liaquat National Hospital.

Patients will be randomly allocated into two groups according to lottery method. The randomization process will be performed using random allocation and patients divided in ratio 1:1. Patients will be randomly assigned to one of the two study groups; group one (tamsulosin), and group two (solifenacin)

on the day of the surgery after placement of the stent. Patients in group 1 will receive tamsulosin capsule (Brand: Cap Tamsolin) 0.4 mg/day, while patients in group 2 will receive solifenacin tablet (Brand: Tab Solifen) 5 mg/day. The cost will be borne by the patient as these medications are routinely given to the patient post DJ stenting, irrespective of their participation in the study. The medication will be taken until removal of the stent. Patients will be reviewed 2 weeks after stenting in opd. The USSQ is the only validated scoring system for evaluation of ureteral stent-related symptoms [9] and therefore has to be used for comparing different treatments for alleviation of these symptoms. USSQ translated into Urdu will be used for patients who are unable to answer questionnaire in English [10].

DATA ANALYSIS PROCEDURE:

Patient's data will be compiled and analyzed through statistical package for Social Sciences (SPSS) Version 25. Normality of the data will be checked by Shapiro wilk's test. Mean \pm SD will be calculated for quantitative variable for groups i.e. age, height, weight, body mass index, length of stent placed and total USSQ score. If the data is non normal, median (iqr) will be reported instead of mean \pm SD. Frequency and percentage will be computed for qualitative variables for groups like gender, any addiction, diabetes, hypertension, smoker, occupation, surgical procedure and indications of stent placement. ANOVA will be applied to see the mean differences between groups. Chi square test or Fischer exact test will be used for finding association between categorical variables. Post stratification will be done on age, gender, height, weight, body mass index, any addiction, diabetes, hypertension, smoker, occupation, surgical procedure and indications of stent placement to see the effect of these modifiers on outcome. P-value ≤ 0.05 will be considered as significant.

ETHICAL CONSIDERATION:

Conducting a randomized control trial (RCT) comparing alpha-blocker and anti-cholinergic drugs involves several ethical considerations. It's crucial to prioritize the well-being and rights of participants while ensuring scientific rigor. Here are some ethical concerns associated with this a trial:

1. Informed Consent:

Ensuring that participants fully understand the nature of the study, potential risks, benefits, and alternatives before providing informed consent. It will be clearly communicated that participation is voluntary, and individuals have the right to withdraw at any time without facing negative consequences.

2. Participant Selection and Equity:

Ensuring that the selection criteria for participants are fair and do not disproportionately exclude certain demographic groups, potentially leading to biased results.

3. Confidentiality and Privacy:

Safeguarding participant confidentiality and privacy by implementing robust data protection measures. Clearly communicating how participant data will be handled, stored, and shared to maintain trust and comply with relevant privacy regulations.

4. Publication and Reporting:

Committing to transparent and timely reporting of study results, whether positive or negative, to contribute to scientific knowledge and prevent publication bias.

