10. Mirani K K, Ather M H (August 08, 2022) Translation and Validation of the Ureteral Stent Symptoms Questionnaire in Urdu. *Cureus* 14(8): e27764. DOI 10.7759/cureus.27764

ANNEXURE-I PROFORMA

GROUP: _____

Serial No: _____

Case No: _____

Patient's Name: _____

Patient's contact #: _____

S/O, D/O, W/O: _____

Patient's Age: _____ years

Gender: Male Female

Height: _____

Weight: _____

BMI: _____

Any Addiction: Yes No _____

Diabetes: Yes No

Hypertension: Yes No

Smoker: Yes No

Occupation: _____

Surgical Procedure: _____

Indication of stent placement: _____

Date of stent placement: _____

Length of stent placed: _____ (cm)

Total USSQ score: _____

ANNEXURE-II USSQ(Stent in situ)

We are interested to know about various aspects of your health, following insertion of the stent and the effect the stent has had on your health.

**Please complete the following questionnaire, which has different sections.
Please answer all questions in each section.**

(We would be grateful if you could complete and post the questionnaire within seven days)

Please complete:

Today's Date: / /

Date of Birth: / /

You will see that some questions ask if you have a symptom occasionally, sometimes or most of the time.

Occasionally	=	less than one third of the time
Sometimes	=	between one and two thirds of the time
Most of the time	=	more than two thirds of the time

URINARY SYMPTOMS

Please answer the questions thinking about the urinary symptoms you have experienced following insertion of the stent.

Please put a tick in one box for each question

Please think about your experience since insertion of the stent.

U1. During the day, how often do you pass urine, on average?

Less than hourly	 5	Every 3 hourly	 2
Hourly	 4	Every 4 hours or more	 1
Every 2 hourly	 3		

U2. During the night, how many times do you have to get up to pass urine, on average?

None	 1	3	 4
1	 2	4 or more	 5
2	 3		

U3. Do you have to rush to the toilet to urinate?

Never	 1	Most of the time	 4

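### Does the Setting sentence about patients with voiding complaints mean that patients are selected on the symptoms the USSQ measures?

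*Combined protocol and SAP*

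**What the plan says.** Four places bear on who enters the trial.

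- **Setting (Material and Methods):** "It will include the patients who had have complaints voiding symptoms like increased urinary frequency, urgency dysuria". The list continues with incomplete bladder emptying and suprapubic pain. No time point or threshold is given.
- **Inclusion and exclusion criteria:** inclusion needs age 20 to 50 years and consent to a unilateral DJ stent for ureteric calculi or after ureteroscopic lithotripsy. One exclusion is "Having a history of LUTS before DJ stent placement".
- **Data Collection Procedure, enrolment:** "Patients fulfilling the inclusion criteria presenting via outpatient clinic or emergency department at Liaquat National hospital, will be included in the study", after written consent. Sampling is stated to be consecutive.
- **Data Collection Procedure, timing:** patients are allocated "on the day of the surgery after placement of the stent", and the follow-up is "Patients will be reviewed 2 weeks after stenting in opd".

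The same section adds that both drugs are routine after stenting whether or not the patient takes part. The operational definition of LUTS covers frequency, urgency and incomplete emptying, which are three of the five complaints named in Setting. The USSQ in Annexure II asks about all five: U1 (frequency), U3 (urgency: "Do you have to rush to the toilet to urinate"), U6 (emptying), U7 (burning) and P2/P3 (bladder-area pain).

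**The concern.** Taken as an entry rule, the Setting sentence does not fit the rest of the plan. A patient with frequency, urgency or incomplete emptying before the stent satisfies Setting but is barred by the LUTS exclusion. For those three complaints the sentence could therefore be met only by symptoms that arise after the stent. Allocation follows stenting on the same day, so most such symptoms would appear after treatment had started. Dysuria and suprapubic pain are not in the plan's LUTS list and could be present earlier.

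If complaints were judged after allocation, patients doing well would be dropped. If solifenacin is the better drug, as hypothesised, more would be lost from that arm. The groups compared would no longer be the groups randomised, and the observed difference would be too small. A reader might also be unsure whether the result describes all stented patients or only those with symptoms.

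**Working it through.** **Step 1. The plan's own figure.** The sample size section gives USSQ means of 76 (SD 8) on tamsulosin and 61 (SD 8.8) on solifenacin, 90% power and 95% confidence. Two-sided, n per group = (8² + 8.8²)(1.960 + 1.282)² / 15² = 6.61, rounded up to 7, or 14 in total as stated. With the planned 30 per group, power at that difference exceeds 99.9%. Sample size is not the issue.

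**Step 2. When could the sentence matter?**

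| When complaints are judged | Effect on the comparison |
|---|---|
| Not judged; the eligibility lists are followed | None |
| Before allocation | Arms stay comparable; narrower population, and conflict with the LUTS exclusion for three complaints present before the stent |
| After treatment starts | Arms selected on the outcome; difference shrinks |

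Only the last row biases the comparison between arms.

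**Step 3. Size of the last row.** The plan gives no threshold, so this is an illustration. Assume normal scores with the means and SDs above, and that a patient is kept only if the total USSQ score exceeds a cut-off c. With a = (c − m)/s, the share kept is 1 − Φ(a) and the mean of those kept is m + s·φ(a)/(1 − Φ(a)).

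Worked example, c = 60:

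- Tamsulosin: a = (60 − 76)/8 = −2.00; kept 0.977; mean 76 + 8 × 0.0552 = 76.4.
- Solifenacin: a = (60 − 61)/8.8 = −0.114; kept 0.545; mean 61 + 8.8 × 0.727 = 67.4.
- Difference: 9.0.

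| Cut-off | Kept of 30, tamsulosin | Kept of 30, solifenacin | Difference |
|---|---|---|---|
| 45 | 30.0 | 29.0 | 14.3 |
| 50 | 30.0 | 26.8 | 13.2 |
| 55 | 29.9 | 22.6 | 11.4 |
| 60 | 29.3 | 16.4 | 9.0 |

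**Step 4. Which cut-offs are plausible?** The background gives symptom rates in stented patients: frequency 50–60%, urgency 57–60%, dysuria 40%, incomplete emptying 76%, suprapubic pain 30%. Assume these rates hold in the trial and that those dropped are the lowest scorers.

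- *Most that could lack all five:* 1 − 0.76 = 24%. This needs every patient with another listed complaint to have incomplete emptying too. Dropping 24% over both arms corresponds to c = 60.0 and a difference of 9.0; shrinkage (15 − 9.0)/15 = 40%.
- *If the five were independent:* 0.40 × 0.40 × 0.60 × 0.24 × 0.70 = 1.6% up to 0.50 × 0.43 × 0.60 × 0.24 × 0.70 = 2.2%. This corresponds to c between about 44.7 and 45.9 and a difference of 14.3 to 14.2; shrinkage of about 5%.

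At the 40% end, 29.3 and 16.4 patients remain, with SDs of 7.53 and 5.49 after truncation. The standard error is √(7.53²/29.3 + 5.49²/16.4) = 1.94, and 9.04/1.94 = 4.66. Welch power is about 99.5%.

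**Step 5. Does the plan describe the last row?** No section does. Enrolment refers to the inclusion criteria, sampling is consecutive, the drugs are routine after stenting with no symptom condition mentioned, and the proforma in Annexure I has no field for symptoms at entry. The plan contains neither a symptom screen nor a rule for removing allocated patients who have few complaints.

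**The case for a change.** The strongest reply is that the inconsistency is real and cheap to correct. The sentence uses enrolment wording inside Material and Methods, it collides with the LUTS exclusion for three complaints, and nothing expressly forbids its use. Because Annexure I does not record entry symptoms, nobody could check later whether it had been applied. The analysis section also does not say that every allocated patient is analysed in the assigned group.

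The mismatch stands, and the sentence could be worded better. The rest carries less weight. The missing proforma field counts at least as much against a symptom screen as for one, since a study that screened on symptoms would need somewhere to record them. The missing statement on analysing patients as allocated is a general gap that exists with or without this sentence, and it should be judged on its own. The doubt about the target population is answered by the eligibility lists, which define it as stented patients without prior LUTS.

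The 40% figure is also the far end of a range. It needs the least favourable overlap of symptoms and removal of exactly the lowest scorers. The total score also covers general health, work, sexual matters and additional problems, so it is a poor stand-in for having a voiding complaint. The wording in Setting is illustrative, so other complaints would qualify and fewer patients would be dropped.

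**Conclusion.** The concern does not call for a change to the plan. The Setting sentence disagrees with the eligibility lists, but the plan states elsewhere which rule governs entry, and under that rule this sentence has no effect on the comparison. Bias would need a step that no section describes: randomising and treating patients, then removing those with few symptoms.

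If that were done, the 15-point difference would fall to between about 14.3 and 9.0 (5% to 40%), assuming normal scores, the background symptom rates and removal of the lowest scorers. The error would be toward no difference, with power still about 99% at the far end, so it would understate a solifenacin benefit and not create one. This conclusion rests on staff following the written inclusion and exclusion criteria, which is the natural reading. Rewording or removing the sentence would be a clerical improvement that alters no result.

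### Two stent indications are pooled, but neither the lottery nor the main USSQ comparison takes indication into account: a loss of precision, not a bias

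*Combined protocol and SAP*

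**What the plan says.** - **Entry (Inclusion criteria).** One criterion covers two situations: a unilateral stent "to relieve upper urinary tract obstruction caused by ureteric calculi or after ureteroscopic lithotripsy for ureteral calculi". In the second the stone has been treated. For the first, no stone treatment is named.
- **Setting (Rationale).** The population is described more broadly, as "Dj stenting prior to Extracorporeal shockwave lithotripsy (ESWL), Ureteroscopy (URS) with DJ stent placement or Percutaneous nephrolithotomy (PCNL) with DJ stent placement".
- **Allocation (Data Collection Procedure).** "Patients will be randomly allocated into two groups according to lottery method". The ratio is 1:1, and no strata or blocks are named. The draw takes place "on the day of the surgery after placement of the stent", so indication is already known.
- **Analysis (Data Analysis Procedure).** Group means are compared by ANOVA, with no covariate named. Surgical procedure and indication are to be tabulated by group. They are also two of 12 post-stratification variables, examined as modifiers of the outcome. No model or combined adjusted estimate is given.
- **Data (Annexure I).** The proforma records surgical procedure, indication and one total USSQ score. It has no line for a stone procedure after stenting and no second USSQ field for a baseline score.

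**The concern.** Patients whose stent relieves an obstruction and patients recovering from ureteroscopic lithotripsy may score differently on the USSQ whichever drug they take. Some items do not ask the patient to attribute the symptom to the stent: visible blood (U8, U9), kidney-area pain on voiding (P7), tiredness (G3) and suspected infection (A1).

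If the indications do differ, there are two consequences. A chance difference in mix between the arms carries over into the drug difference of that particular trial. And the spread between indications stays in the error term, so the confidence interval is wider than it need be. Post-stratification displays the strata one at a time and changes neither feature of the main comparison. With no baseline score, baseline adjustment cannot absorb the difference either. An adjustment added only after an imbalance has been seen would be open to the charge of being data-driven.

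**Working it through.** **Inputs from the plan (Sample size).** "76 \pm 8 in tamsulosin group and 61 \pm 8.8 in solefinacin group", 90% power, 95% confidence, 7 per group calculated, 30 per group planned. Two-sided 5% is assumed because the sidedness is not stated.

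**Inputs not in the plan, therefore assumed.** The share of each indication and the USSQ gap D between them.

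**1. The plan's own figure.**
- Pooled SD = √((8² + 8.8²)/2) = √70.72 = 8.41; difference = 76 − 61 = 15.
- n per arm = 2 × [8.41 × (1.960 + 1.282)/15]² = 6.61, rounded up to 7, so 14 in total. This matches the plan.

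**2. Chance of an uneven mix.** With arms of exactly 30, the number in one arm with the less common indication is hypergeometric (60 patients, K with that indication, 30 drawn). A difference of 20 percentage points or more means |2x − K| ≥ 6.

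| Share of less common indication | K | P(≥ 20 points), 30/30 | P(≥ 20 points), coin-toss allocation |
|---|---|---|---|
| 20% | 12 | 10% | 6% |
| 30% | 18 | 16% | 10% |
| 50% | 30 | 20% | 15% |

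A difference of 30 points or more occurs in at most 3% of trials under either scheme.

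**3. What a 20-point imbalance does.** Shift in the drug difference = D × 0.20. For D = 4, 8, 12 this is 0.8, 1.6, 2.4 points. The standard error is 8.41 × √(2/30) = 2.17.

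**4. Precision.** Suppose 8.41 is the SD within an indication and the mix is 50/50. Ignoring indication adds D²/4 to the variance. Half-width = t(0.975, 58) × SD × √(2/30), with t = 2.00.

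| D | Variance | SD | 95% CI half-width |
|---|---|---|---|
| 0 | 70.72 | 8.41 | 4.35 |
| 4 | 74.72 | 8.64 | 4.47 |
| 8 | 86.72 | 9.31 | 4.81 |
| 12 | 106.72 | 10.33 | 5.34 |

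**5. Error rates over the whole lottery (simulation, 30/30, 50/50 mix).**
- With no drug effect and gaps of 0 to 15 points, the unadjusted test rejects in 4.8% to 5.2% of 20,000 trials per gap, and the average estimate is essentially zero.
- With an illustrative true difference of 6 points, unadjusted power is 74%, 65% and 53% for gaps of 5, 10 and 15. Adjusted for indication it is about 77% throughout.
- With no gap, power at 6 points is 78% unadjusted and 78% adjusted, so the covariate costs almost nothing when it is not needed.
- At the planned 15 points, power exceeds 99.9% either way.

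**The case against.** The case against is that this is an ordinary broad-entry design. The Data Collection Procedure says both drugs are routinely given after stenting, so pooling indications is a legitimate choice. Randomisation protects the comparison on average, indication is tabulated by group so an imbalance would be seen, and at the planned effect nothing changes. All of that stands. It limits the size of the point, but does not explain why a recorded variable, known before allocation, is left out of the main model.

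It is also fair that the widening in step 4 depends on reading 8.4 as a within-indication SD. If it is the overall SD, the spread is already inside the 4.35, and adjustment would narrow the interval instead. The direction of the gain is the same.

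A reader might infer more than the documents support:

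- **That a drug difference could really be a difference in stone course.** Producing 15 points by mix alone would need a 100-point imbalance at a gap of 15. At a gap of 12 it would need 125 points (15/12), which is impossible.
- **That a remaining stone or an ESWL session raises the USSQ as much as the stent does.** Nothing in the documents says so. The instruction "Please think about your experience since insertion of the stent" opens the urinary section only. Pain sites (P2), painkillers (P8), days in bed (W2), antibiotics (A2) and hospital visits (A4) are all worded as due to the stent. Patients may attribute imperfectly, but by how much is unknown.
- **That ESWL falls before the 2-week review.** The entry criterion does not name ESWL. It comes from the Rationale, and no section says when a stone still in place is treated.

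**Conclusion.** The point holds as a matter of efficiency and of protection against an unlucky draw. The plan pools two indications and ignores them in both the lottery and the main comparison, although the information is in hand at allocation. The type I error and the average estimate are sound.

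Under the assumed gaps of 4 to 12 points, the cost is a shift of 0.8 to 2.4 points in the minority of trials with a 20-point imbalance, and a half-width larger by 0.12 to 0.99 points at a 50/50 mix. If the true difference is near 15 the conclusion is safe. If it is nearer 6, the loss of power can be material. The indication gap and mix are assumptions throughout; if the gap is negligible, so is the gain.

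**What to change.** 1. **Analysis.** Prespecify the main comparison of total USSQ as a linear model (two-way ANOVA) with drug and indication, and report the adjusted drug difference with its 95% CI. Define the two indication levels in advance. Keep the other post-stratification variables exploratory.
2. **Allocation.** Draw lots separately within each indication, using sets with equal numbers of lots per drug, or blocks. Two simple lotteries without such sets would not guarantee balance.
3. **Data.** Add one proforma line for any stone procedure between stenting and the USSQ, for description only. It arises after allocation, so it should not be a covariate.
4. **Timing.** Keep the common 2-week assessment. Completing some forms earlier would make the windows unequal, and items that count days, courses or visits since insertion (W2, W3, A2 to A4) would score lower simply because less time had passed.

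The cost is one degree of freedom, a second set of lots, one extra factor in SPSS and one proforma line. The last unfinished set in each indication may leave a small residual imbalance, which the model handles. The sample size stays at 30 per arm.

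### Low severity, patient safety only: no eligibility criterion requires that a patient can take both study drugs, although a lottery decides which one is assigned

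*Combined protocol and SAP*

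**What the plan says.** The eligibility lists are short and fully readable.

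- **Inclusion criteria:** age ("Between the ages of 20 and 50 years") and consent to a unilateral DJ stent, either for obstruction by ureteric stones or after ureteroscopic lithotripsy.
- **Exclusion criteria:** prior urinary symptoms ("Having a history of LUTS before DJ stent placement"), bilateral stents, and stent displacement.

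Under Data Collection Procedure, patients who meet the inclusion criteria "will be included in the study after taking informed and written consent". Then: "Patients will be randomly allocated into two groups according to lottery method". The same section adds: "Patients will be randomly assigned to one of the two study groups; group one (tamsulosin), and group two (solifenacin"). The ratio is 1:1, and assignment takes place on the day of surgery once the stent is in. Group 1 takes tamsulosin 0.4 mg daily and group 2 solifenacin 5 mg daily, until the stent comes out. The follow-up step is: "Patients will be reviewed 2 weeks after stenting in opd".

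Several statements elsewhere bear on safety. Data Collection Procedure says that "these medications are routinely given to the patient post DJ stenting, irrespective of their participation in the study" and requires ethics approval. Ethical Consideration promises disclosure of risks and alternatives at consent and a right to withdraw at any time. It also directs patients with an adverse event to the hospital's emergency department, and reports that the team has seen no adverse effect so far.

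**The concern.** In a randomised comparison of two active drugs, each participant should be someone for whom either drug is acceptable, because the draw and not a clinician selects the treatment. Eligibility criteria normally secure this before allocation. Here no criterion mentions allergy, intolerance, contraindication, interacting medicines or a physician's judgement about either drug. The procedure goes from meeting the criteria, to consent, to the lottery.

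What is at stake is the safety of the individual patient. Someone known in advance to be unsuitable for one drug could be randomised to it, and the plan has no rule for what happens next. Ethical Consideration makes participants' well-being a priority, and the eligibility list is the natural place to act on that before the first dose.

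**Working it through.** **1. Reading the criteria against the requirement**

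| Criterion | Concerns suitability for a study drug? |
|---|---|
| Age 20 to 50 | No |
| Unilateral stent, consented | No |
| No prior LUTS | No; narrows the population but is about symptoms |
| No bilateral stents | No |
| No stent displacement | No |

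The proforma (Annexure-I) records diabetes and hypertension, but Data Analysis Procedure uses them for description and stratification, not for entry. The proforma has no field for drug allergy or current medicines.

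**2. What the 1:1 ratio implies**

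The inputs are the 1:1 lottery (Data Collection Procedure) and the enrolment target under Sample size, "we will have 30 patients in each group", so 60 in total.

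- A patient unsuitable for exactly one drug is allocated to it with probability 1/2 = 50%.
- If k such patients enrol, the chance that at least one is allocated to the wrong drug is 1 − 0.5^k: 50% for k = 1, 75% for k = 2, 87.5% for k = 3.
- With exactly 30 per group and all k patients unsuitable for the same drug, the figures hardly move: for k = 2, 1 − (30×29)/(60×59) = 75.4%; for k = 3, 1 − (30×29×28)/(60×59×58) = 88.1%.

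These are properties of the draw, given that such patients enrol. They do not say how many will.

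**3. Illustration under an assumed rate**

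The documents give no rate. Let p be the share of eligible patients known to be unsuitable for exactly one drug, with 1% to 5% assumed purely to show scale.

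| p (assumed) | Expected unsuitable allocations, 60 × p/2 | At least one, 1 − (1 − p/2)^60 | Eligible patients needed to enrol 60, 60/(1 − p) |
|---|---|---|---|
| 1% | 0.3 | 26% | 60.6, so 61 |
| 2% | 0.6 | 45% | 61.2, so 62 |
| 5% | 1.5 | 78% | 63.2, so 64 |

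**4. Would the extra criterion strain the sample size?**

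The plan's own figure reproduces. With means 76 and 61 and SDs 8 and 8.8, the common SD is √((8² + 8.8²)/2) = 8.41. Then n = 2 × [8.41 × (1.960 + 1.282)/15]² = 6.61, so 7 per group and 14 in total, as stated (two-sided 5% is assumed, since the plan does not state sidedness). On the same inputs, power at 30 per group exceeds 99.99%, and it still does if 20% of patients were screened out and not replaced (24 per group). The point does not depend on this calculation; it shows only that the fix costs no power on the plan's own terms.

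**The case against.** The best case against runs as follows. Both drugs are described as routine after stenting, and the team reports no adverse effect to date. Patients hear about risks and alternatives, may withdraw at any time, can come to the emergency department, and are seen at 2 weeks. Ethics approval is required. The LUTS exclusion, which by the plan's definitions covers hesitancy, poor stream and incomplete emptying, already removes patients with known voiding problems. Nothing in the text obliges a urologist to give a drug known to be unsuitable, and clinicians may well screen informally.

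Much of this stands, and it is why the severity is low. It does not remove the point, because none of these provisions is a check before the draw. Routine use of the drugs does not make every patient suitable for both. The favourable experience is informal, and the documents do not say that it came from lottery-assigned treatment. Consent and withdrawal rely on the patient recognising the problem.

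A reader might be tempted by stronger readings, which the documents do not support:

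- **That patients will be given a contraindicated drug, perhaps for 14 days until review.** Allocation is not dosing. The plan does not say what a clinician does with an unsuitable allocation, and patients may report a problem or withdraw sooner.
- **That particular groups, such as pregnant or breast-feeding women, are at risk.** The documents name no contraindication for either drug and do not mention pregnancy or breast-feeding, so none is asserted.
- **That the consent material is deficient.** Consent pages were removed before review, so the point concerns the eligibility list and the described procedure only.
- **That the results would be biased or underpowered.** Nothing in the documents supports a material effect of either kind.

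**Conclusion.** The point holds as a low-severity, inexpensive improvement on patient safety grounds. The entry rule as written admits a patient known to be unsuitable for one study drug, and the 1:1 lottery then assigns that drug with 50% probability. That 50% is the only firm number. How many such patients there would be is unknown and probably small. The 0.3 to 1.5 expected unsuitable allocations among 60 rest wholly on the assumed 1% to 5% and should not be read as an estimate, and the severity of any resulting harm cannot be judged from the documents. That a clinician outside the trial could simply choose the other drug is a reasonable inference, not something the plan states.

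**What to change.** Add one exclusion: *known hypersensitivity or any contraindication to tamsulosin or solifenacin according to the local product label*. Have the treating physician confirm before the lottery that the patient may receive either drug; one line on the proforma would record it.

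The cost is one criterion and one confirmation, with no extra staff or procedure. The downside is that a few otherwise eligible patients are not enrolled: under the assumed 1% to 5%, 61 to 64 eligible patients would be needed to enrol 60, that is 1 to 4 extra. Tying the wording to the label and the physician's judgement, without a blanket exclusion of any group, respects the commitment to fair selection in Ethical Consideration, although label advice could still fall more on some patients than others. The check finds only what is known before the draw.
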